## **Statement of the risks/benefits** for the study subjects.

How **privacy, confidentiality** and the rights of human subjects will be protected. In order to safeguard the privacy of study participants, protected identifiers (e.g., a person's name) normally should not be recorded on the same instrument where you record data obtained from study subjects. A justification must be made in the protocol as to why the research cannot be conducted in any other way if you believe you need both protected identifiers and information obtained from subjects on the same data collection form.

### *Risk and benefits for study participants*

Although participants may not directly benefit from being in this study, future caregivers might benefit because the aim of the project is to develop and test the potential benefits of culturally tailored educational videos for home hospice caregivers.

There are minimal risks participants might experience from being in this study. Participants may feel uncomfortable answering certain questions or watching the videos. If this occurs, participants can choose to stop participating at any time. There is always a risk that the data collected may be stolen or breached. However, there are safeguards in place to minimize this risk (see privacy and confidentiality section).

### *Privacy and confidentiality*

Data entry (e.g., demographic data, answers to survey questions) will be done using Weill Cornell REDCap database, a secure web-based application hosted by the Weill Cornell Clinical and Translational Science Center. Data entry will be conducted at the time of the video visit with participants in order to eliminate the risk of stolen or lost data during transportation. Video visits with participants will be conducted over Zoom which is HIPAA compliant.

Any audio files collected from focus groups/interviews will be transferred and stored on the PI's password protected computer which is protected on Weill Cornell Medicine's secure server.

Only members of the research team will have access to the materials. All protected identifiers will not be recorded/entered on the same instrument where record data will be obtained from study subjects.

For studies that require a DSMB, a **DSMB plan** should be provided in the protocol which should include: number of members, meetings (how often), data that will be reviewed during the meetings and plan regarding dissemination of summary reports (i.e. meeting minutes) to the IRB.

\*\*\*Below is the DSMP that was submitted with the grant. We did not receive any comments about needing to add a independent member to the DSMP given the minimal risk of the study. Please let me know if this will suffice. Thank you.\*\*\*

## DATA AND SAFETY MONITORING PLAN

### PI of Grant: [name], MS

**Title:** Developing and pilot testing culturally based educational videos for Puerto Rican and African American home hospice caregivers.

**Brief Description of Intervention:** Using experience based co-design, culturally based videos will be developed and piloted among Puerto Rican and African American home hospice caregivers.

**NIH Phase III Clinical Trial?** No

**Multiple Site Trial?** Yes

#### Specific Aims:

**Aim 1:** *To gather input, through interviews and focus group methodology, from Puerto Rican and African American family caregivers to understand culturally based views and knowledge gaps around symptom related issues in home hospice care.*

**Aim 2:** *To develop 12 video scripts, using experience based codesign, with input from a stakeholder group (e.g., family caregivers, hospice physician/nurse practitioner, nurse, social worker, chaplain). Scripts will be used to produce educational videos on symptom related issues for Puerto Rican and African American caregivers.*

**Aim 3:** *To pilot caregiver educational videos with Puerto Rican (n=10) and African American (n=10) family caregivers receiving home hospice care. Caregivers' comfort in dealing with symptom related issues, level of preparedness and self-efficacy will be assessed, pre and post intervention, along with its perceived usefulness and limitations.*

#### Brief Description of Project Design

For Aim 1, symptom related issues will be elicited from Puerto Rican (N=15) and African American N=15 family caregivers using experience based co-design.

For Aim 2, stakeholder groups will be recruited to develop videos scripts which will be used to produce educational videos on symptom related issues for Puerto Rican and African American caregivers.

For Aim 3, a pilot study will be conducted to show these caregivers related videos to Puerto Rican and African American caregivers and collect data pre and post intervention.

## A. PARTICIPANTS SAFETY

### A.1 Adverse Event and Serious Adverse Event Collection and Reporting

I have identified two categories of adverse events: serious adverse events and safety alerts. Members of the research team will be trained to track these events through observation and interaction with participants (patient and/or caregiver). Adverse events are situations that occurred during the study/intervention period and are identified by members of the research team during any assessment or any off-protocol interaction with a participant. Adverse events occur anytime following enrollment until study completion. Safety alerts will be identified during any interview or anytime following enrollment until study completion.

Below are the specific events that trigger a formal response:

#### Serious Adverse Events

- Hospitalization of participant
- Institutionalization of participant
- Emergency room visit of participant

#### Safety Alerts

- Participant threatens to harm him or herself or others

A summary of all serious adverse events and safety alerts (i.e., those that are anticipated and related to the study) will be reported to the NIA Program Officer and Safety Officer quarterly, unless otherwise requested by a Safety Officer.

When serious adverse events occur that are unanticipated (i.e., events that are not listed above) and are related to the study (i.e., there is a reasonable possibility that the incident, experience, or outcome may have been caused by the procedures involved in the research), they will be reported to the NIA Program Officer within 48 hours of the study's knowledge. Unanticipated problems involving risks to study participants or others will also be reported to NIA within 48 hours. Unanticipated problems are defined as any incident, experience, or outcome that is unexpected given the research procedures that are described in the protocol-related documents; related or possibly related to participation in the research; or suggest that the research places participants at a greater risk of harm than was previously known or recognized.

[name], the PI, will be responsible for ensuring participants' safety on a daily basis. He will also evaluate the progress of the study, review procedures for maintaining the confidentiality of data, the quality of data collection, management, and analyses.

### A.2 Frequency of Data and Safety Monitoring

When a safety alert or adverse event is identified by a member of the research team, the event must be reported to [name] within 24 hours and recorded on the Alert/Adverse Event Form in the study's REDCap database. [name] will report any adverse events related to the study to the VNSNY IRB, according to IRB policy. When serious adverse events occur that are unanticipated (i.e., not listed in the Data and Safety Monitoring Plan) and that are related to the study, they will be reported to the NIA Program Officer within 48 hours of the study's knowledge of the serious adverse event.

### A.3 Protection Against Study Risks

#### Informed Consent

Screening of potentially eligible participants (hospice caregivers and staff) will be conducted virtually by a study staff member using an IRB-approved screening template. Study staff will explain the study and answer any questions.

If the participant agrees to be part of the study, a virtual visit will be conducted where a member of the research staff will review the study and the participant will be asked to sign an electronic informed consent. A copy of the consent will be provided to the participant. Participants enrolled in the study will then undergo a baseline interview and proceed with the study protocol as outlined in the other sections of the grant. Throughout the study period and with each interaction with the study team, each participant will be encouraged to ask questions and told that even if they consent to be in the study, they are free to withdraw from it at any time, for any reason.

The main points that will be addressed by study staff obtaining informed consent include: explaining why the current research study is being conducted, the source of funding for the project, and what purpose the proposed research serves. Additionally, the subject will be made aware of who is responsible for conducting the research as well as how participants, including themselves, are selected for participation in the research.

The study staff will explain in detail what will be asked of the participants if they agree to participate in the study and estimate the potential time commitment involved. Participants will know what their responsibilities will entail, what risk or benefit may be involved and what potential costs could be incurred should they agree to participate. The study staff will underscore the importance placed upon maintaining participant confidentiality as well as their rights while involved in the study, which includes the right to withdraw participation at any time during the research due to the fact that their participation is entirely voluntary in nature.

The informed consent will also contain a section dedicated to explaining what constitutes protected health information and how this information remains confidential per HIPAA (Health Insurance Portability and Accountability Act) guidelines.

Finally, the informed consent will provide contact information for both Principal Investigators, the Office for the Protection of Research Subjects, and the Site PI contact. All informed consent processes will adhere to the policies set forth by the Institutional Review Board. All informed consent forms will be stored in a locked file cabinet or locked computer file in a locked office to maintain the privacy of all study participants.

In summary, the consent form will include a description of all study procedures, information regarding the risks and benefits of participation, contact information for study staff who can answer participants' questions, and alternatives to participation in the study. The consent form will also state that: (1) participation is voluntary, (2) participants can refuse to answer any questions, (3) participants can withdraw from the study at any time, (4) all responses will remain confidential, and (5) participation in the study is not related to care received while in hospice.

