### **Aim 1**

Aim 1 will consist of individual interviews and/or focus groups (dependent on participant preference and availability) conducted with Puerto Rican and African American family caregivers who have been discharged from home hospice care (n=15 for each group). Family caregivers will be recruited from the Visiting Nurse Service of New York (VNSNY) hospice organization, Hospicio Toque de Amor, and Hospicio Luz Celeste.

The research team will work collaboratively with hospice leadership at each site to generate a recurring list of home hospice patients who have been discharged over the prior six months. This list will contain contact information (e.g. name, phone number) of the listed family caregiver along with the name, race/ethnicity and age of the hospice patient for recruitment purposes. In order to be mindful of the sensitive nature recruiting caregivers immediately after a hospice discharge, a research member will wait one month from the care recipient's discharge date before contacting the family caregiver for participation.

Caregivers will be contacted by phone and those who qualify for the study and express interest in participating will be scheduled for either a focus group session or an individual interview, based on caregiver preference and schedule. Both methods will be conducted either virtually using teleconference software or in-person at the participant's residence. Electronic informed consent will be obtained for virtual participation and signed paper informed consent will be obtained for in-person participation prior to enrollment into the study. Demographic data will also be collected from each caregiver participant after enrollment which will include: age, gender, religion, birthplace, education level, relationship to patient, occupation, average number of hours spent caregiving per week when receiving hospice care. We will also contact the collaborating hospices to collect the hospice diagnosis of their care recipients.

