### **Aim 2**

Aim 2 will use principles of experience based co-design (EBCD) as part of the study design. EBCD is an approach that engages patients/caregivers and healthcare staff in partnership to develop and improve health services or pathways of care. For this study, the EBCD model will consist of bringing family caregivers and hospice staff together to share in their experiences and work on the study's aim through an iterative process.

Puerto Rican and African American stakeholder group (i.e., caregivers, hospice nurses, nurse practitioners, physicians, social workers, spiritual counselors) will be recruited from VNSNY hospice, Hospicio Toque de Amor, and Hospicio Luz Celeste. The research team will work collaboratively with hospice leadership at each site to identify potential participants for Aim 2. Participants in Aim 1 of the study who express interest in being contacted to participate in Aim 2 will also be recruited. Participants who express interest in participating as a stakeholder member will be contacted by phone or email to schedule a time to meet. These group meetings will be conducted virtually using teleconference software or in-person meeting or a combination of both (some participants being in-person and some using teleconference software). This will be dependent on the preference of the participants and availability of the research staff member conducting the study. Electronic informed consent will be obtained for virtual participation and signed paper informed consent will be obtained for in-person meetings at the time of study enrollment.

Each stakeholder group (i.e., Puerto Rican and African American) will consist of three family caregivers, a physician or nurse practitioner, nurse, social worker, and spiritual counselors. In these meetings, the research team will present to the group the four symptom related issues generated from Aim 1. The group will work collaboratively together and with the research team to create video scripts that incorporate symptom related concerns shared by caregivers with culturally based views, practices, and beliefs. Each member of the group will play a critical role in bringing their own experiences and perspective to help shape the content of the video scripts. The goal of the meetings will be to create tailored messaging that aims to enhance understanding and knowledge for Puerto Rican and African American caregivers.

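### The consent form is to promise confidentiality for every response without exception, but in Aim 2 meetings and Aim 1 focus groups other participants hear what is said, so the team cannot keep that promise

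*Combined protocol and SAP*

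**What the plan says.** The Data and Safety Monitoring Plan, A.3, Informed Consent, closes with a numbered list of statements that the consent form will contain. One of them is "4) all responses will remain confidential". It carries no exception. The section opens with "Screening of potentially eligible participants (hospice caregivers and staff", so it covers both kinds of participant who attend group sessions.

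The group sessions are described under Study design:

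- **Aim 1:** "Aim 1 will consist of individual interviews and/or focus groups (dependent on participant preference and availability". After the phone contact, eligible and interested caregivers are "scheduled for either a focus group session or an individual interview, based on caregiver preference and schedule".
- **Aim 2:** the co-design model consists of "bringing family caregivers and hospice staff together to share in their experiences". No individual format is offered. The eligibility criteria for Aim 2 give 3 caregivers and 4 staff for each of the two groups, with staff drawn from the three recruiting hospices.

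Two other sections bear on confidentiality. Privacy and confidentiality covers the database, the video platform, storage of audio files and the research team's access to materials. Risk and benefits for study participants names discomfort and the theft or breach of stored data.

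**The concern.** A confidentiality statement in a consent form should describe something the study can deliver. The research team controls its own recordings, files and reports. It does not control what a caregiver or a staff member says after leaving a group meeting. A promise that covers every response, made to people who will speak in front of others, therefore goes further than the design allows.

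Aim 2 is the clearest case. Caregivers there speak about symptom problems in front of staff of the hospices from which the study recruits, and those staff may belong to the hospice that cared for the relative. What is at stake is the accuracy of what participants are told. The trial's estimates are not affected.

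**Working it through.** This is a check of the text against itself. The plan gives no figure to reproduce, and the only arithmetic is a head count.

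**Step 1. Scope of the promise.** The prescribed statement covers all responses and applies to caregivers and staff. It is not limited to the research team's handling of data.

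**Step 2. Who hears the responses.** Caregiver and staff numbers come from Sample selection, Aims 1 to 3.

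- Aim 2: 3 caregivers + 4 staff = 7 per group, and 2 × 7 = 14 enrolments. Each member is heard by 7 − 1 = 6 other participants who attend as participants, not as researchers.
- Aim 1: 15 + 15 = 30 caregivers. The number in focus groups depends on preference and schedule and is not predicted, so it lies between 0 and 30.
- Aim 3: 10 + 10 = 20 caregivers. The visits are arranged with each participant, and no group session is described.

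**Step 3. Size.** Total planned enrolments are 30 + 14 + 20 = 64.

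| Aim 1 caregivers in focus groups | Enrolments with group exposure | Share of 64 |
|---|---|---|
| 0 | 14 | 14/64 = 22% |
| 30 | 14 + 30 = 44 | 44/64 = 69% |

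These are enrolments, not people. Aim 1 caregivers may also join Aim 2, so up to 6 people could be counted twice. They count those to whom the promise does not hold as worded. They do not predict how many disclosures would occur.

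**Step 4. Is the promise qualified elsewhere?**

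- Privacy and confidentiality deals with storage and team access. It is silent on what other group members hear.
- Risk and benefits states "Participants may feel uncomfortable answering certain questions or watching the videos" and adds the risk of data theft or breach. Disclosure by fellow participants is not listed.
- The A.3 consent text contains no limit for group sessions and no request that members keep the discussion private.
- The recruitment procedures for Aims 1 and 2 describe scheduling and consent, and mention no such limit. They refer to phone scripts that are not in the file.

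No visible section repairs the conflict between the promise and the group format.

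**The case against.** **The consent form is not visible.** Its pages were removed before review, and the list in A.3 is a summary from a plan submitted with the grant. The same section requires the form to describe all procedures and risks and to follow IRB policy, so a group caveat may already be there. This stands as a limit. A reader might infer that the form itself is defective, and the documents do not show that. If the form is already qualified, A.3 should be brought into line with it.

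**Participants know that a group is a group.** Anyone who attends expects to be heard, and may decline questions or withdraw. That is fair, and it makes surprise in the session unlikely. But knowing that others are present is different from being told that the promise does not extend to them, and withdrawing does not recall what has been said.

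**Confidential may simply mean the team's data handling.** That is probably the intent, but the prescribed wording does not say so.

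**Safety alerts.** A reader might infer that safety reporting also breaks the promise, and for all 64 enrolments. The alert is defined as "Participant threatens to harm him or herself or others", and the plan says "When a safety alert or adverse event is identified by a member of the research team, the event must be reported to" a named person within 24 hours and recorded in the study database. The name is removed, and that person may be within the team. The funder's program officer and the Safety Officer receive a summary, which may be de-identified. No section describes identified disclosure to a third party. A breach is therefore not shown. What remains is that participants should know such reports are made.

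**Choice of format and candor.** A reader might also infer that Aim 1 caregivers choose a group after being assured that privacy is equal, and that lost candor then weakens the videos. The Aim 1 text places the choice at scheduling and requires consent only before enrollment, so that sequence is not documented. The effect on candor is conjecture.

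**Conclusion.** The point holds for the wording that the plan prescribes and for the sessions held in groups. It applies to the 14 Aim 2 enrolments by design and to between 0 and 30 Aim 1 caregivers, depending on how many choose a focus group. It does not apply to Aim 1 individual interviews or to Aim 3 visits.

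It rests on two assumptions. One is that the consent form follows the A.3 list. The other is that each Aim 2 group has 4 staff, as the eligibility criteria state; the study design text mentions spiritual counselors in the plural, which could add to that number.

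This is a stated rule that the design cannot meet, not a missing detail, and it should be corrected. It does not bear on any outcome, sample size or analysis.

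**What to change.** 1. In A.3, Informed Consent, change item (4) so that it says the research team will keep the participant's responses confidential.
2. In the Aim 2 consent and the Aim 1 focus-group consent only, add that other participants (in Aim 2 including hospice staff) will hear what is said, that they are asked to keep it private, and that the team cannot guarantee they will. Leave this out of the Aim 3 and individual-interview consent, where it does not apply.
3. Add disclosure by group members to Risk and benefits for study participants.
4. In Aim 1, under both Study design and the recruitment procedures, have staff state this at the scheduling call, before the caregiver picks a format. In Aims 1 and 2, have it repeated at the start of each group session.
5. As a secondary clarification, mention in the consent that threats of harm are reported as safety alerts, as A.1 and A.2 of the monitoring plan already provide.

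The cost is wording in the consent, the protocol and the phone script. A few more Aim 1 caregivers may choose an individual interview, which the plan already offers.

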## **B. INTERIM ANALYSIS**

No interim analysis is planned, due to the fact that this is a small pilot study of an intervention with minimal risk.

